#### 4.2.4 Replacement of Subjects

Subjects will not be replaced in this study.

### 4.3 Treatment Assignment

An IWRS will be used for assignment of unblinded investigational product to the subject. A subject is considered entered into the study when the investigator notifies the IWRS that the subject meets eligibility criteria and the IWRS provides the assignment of unblinded investigational product to the subject.

The procedure for using IWRS is as follows:

- The investigator or designee contacts the IWRS and provides the SID number and subject's baseline characteristic(s) used to verify the subject's identification
- Confirmation of this information is sent to the investigator/designee who dispenses the assigned treatment to the subject per the communication and records the appropriate information in the subject's medical records and investigational product accountability log

MEDI-575 must be administered within 48 hours after treatment assignment. If there is a delay in the administration of treatment such that it will not be administered within the specified timeframe, the study monitor must be notified *immediately*.

#### 4.4 Blinding

This is an open-label study.

#### 4.5 Study Treatment

##### 4.5.1 Investigational Product Supplies and Accountability

Investigational product will be supplied to the site in open-label containers. Detailed instructions are provided in the Investigational Product Manual.

Investigational product will be distributed to clinical sites using designated distribution centers. MedImmune will provide the investigator(s) with adequate quantities of investigational product. MEDI-575 must be stored in the refrigerator at 2°C to 8°C (36°F to 46°F).

**MEDI-575:** MEDI-575 is supplied in vials as a 20-mg/mL solution, 200 mg/vial for dilution. Formulation: [REDACTED]  
[REDACTED]  
[REDACTED].

**Diluent:** Normal saline, 250 or 500 mL bag (based on subject weight) for dilution of MEDI-575 to be provided by the clinical site.

Specific details regarding investigational product supplies, dose preparation, and accountability will be provided in the Investigational Product Manual supplied to each study site.

The investigator's or site's designated investigational product manager is required to maintain accurate investigational product accountability records. Upon completion of the study, copies of investigational product accountability records will be returned to MedImmune. All unused investigational product will be returned to a MedImmune-authorized depot or disposed of upon authorization by MedImmune (refer to the Investigational Product Manual or other written instructions provided by MedImmune or its designee for contact information and specific shipping instructions).

#### **4.5.2 Treatment Regimens**

Subjects will be treated with MEDI-575 at 25 mg/kg on Day 1 every 21 days until documentation of disease progression, initiation of alternative anticancer therapy, unacceptable toxicity, or another reason for treatment discontinuation (see Section 4.2.3) is observed. In Cycle 2 and beyond, a dose can be delayed up to 7 days for unavoidable scheduling issues. MEDI-575 may be withheld for up to 21 days until resolution to  $\leq$  Grade 1 toxicity after agreement with the sponsor. Subjects who demonstrate stable disease or better may continue to receive MEDI-575 under the criteria above. Each new cycle will begin no fewer than 21 days after the last dose of the previous cycle.

Subjects who receive any number of doses of MEDI-575 and proceed to surgical resection as subsequent therapy for GBM may be asked to allow procurement of resected tissue to determine intratumoral levels of MEDI-575.

#### **4.5.3 Investigational Product Preparation**

The dose of investigational product for administration must be prepared by the investigator's or site's designated investigational product manager using aseptic technique. Detailed instructions regarding investigational product preparation can be found in the Investigational Product Manual that will be provided to the investigator's or site's designated investigational product manager.

The dose of investigational product will be calculated based on the subject's screening body weight (obtained prior to the first administration of MEDI-575). The weight collected at

screening is considered the baseline weight and will be used to calculate the dose of investigational product unless a change in weight of  $\pm 10\%$  occurs. If there is a  $\pm 10\%$  change in weight, the new weight will be used for dose calculation and will be considered the new baseline weight. The dose volume of MEDI-575 will be calculated using the following formula:

$$\text{Dose Volume (mL)} = 25 \text{ (mg/kg)} \times \text{Subject Weight (kg)} \div \text{Concentration (20 mg/mL)}$$

For subjects weighing  $< 140$  kg, MEDI-575 is prepared for administration by dilution into the appropriate volume of normal saline to a final volume of 250 mL. For subjects weighing  $\geq 140$  kg, the final volume will be 500 mL.

To prepare the IV bag, the volume of normal saline equivalent to the calculated dose volume of MEDI-575 is removed from the IV bag, and then the calculated dose volume of MEDI-575 is added to the IV bag containing the remaining saline.

#### **4.5.4 Investigational Product Administration**

The day of receipt of the first dose of MEDI-575 is considered Day 1.

MEDI-575 administration must be completed within 6 hours after IV bag preparation. If the dose cannot be completely administered within 6 hours, a new dose must be prepared using a new vial or vials as the investigational product contains no bacteriostatic agents.

MEDI-575 should be dispensed by the investigational product manager/site pharmacist or qualified designee and administered as an IV infusion. The infusion should be administered over a period of 60 minutes using a protein-sparing/low in-line filter, as specified in the Investigational Product Manual.

##### **4.5.4.1 Monitoring of Dose Administration**

If a subject experiences an infusion reaction during infusion of MEDI-575, an antihistamine such as diphenhydramine (Benadryl®) at 50 mg and acetaminophen (Tylenol®) at 650 mg, or the institutional equivalents, may be administered. Alternatively, or additionally, the rate of infusion of MEDI-575 may be diminished. Any such activities must be recorded appropriately in the source documentation. In subjects who experience an infusion reaction, prophylactic administration of acetaminophen and/or diphenhydramine or the equivalents may be considered for subsequent administration of MEDI-575.

As with any antibody, allergic reactions to dose administration are possible. Therefore, appropriate drugs and medical equipment to treat acute anaphylactic reactions must be immediately available, and study personnel must be trained to recognize and treat anaphylaxis.

#### **4.5.4.2 Dose-limiting Toxicities**

Dose-limiting toxicity rate will be analyzed after the first 15 subjects have completed the first cycle of treatment. If the DLT rate equals or exceeds 30%, further enrollment will be suspended to evaluate safety. The MedImmune SMC will be consulted prior to resumption of enrollment.

The period for evaluating DLTs will be from the time of first administration of MEDI-575 through the first 21-day cycle. Grading of DLTs will be according to the National Cancer Institute Common Terminology Toxicity Criteria for Adverse Events ([Appendix 2](#)).

A DLT is defined as:

1. Any Grade 3 or higher non-hematologic toxicity that occurs during the DLT assessment period and is suspected of a causal relationship to MEDI-575 with the following exceptions:
  - a. Grade 3 fever (in the absence of neutropenia) that resolves to normal or baseline within 24 hours of treatment and is not considered an SAE; or
  - b. Grade 3 rigors/chills that respond to optimal therapy
2. Any Grade 3 or higher hematologic toxicity suspected of a causal relationship to MEDI-575.

#### **4.5.4.3 Dose Modification for Toxicity Management**

Dose modifications of MEDI-575 will be based on hematologic and nonhematologic toxicities that cannot be attributed to another cause such as disease progression or accident following the first cycle of treatment (see [Table 4.5.4.3-1](#)). Both hematologic and nonhematologic toxicities will be graded according to National Cancer Institute's Common Terminology Criteria for Adverse Events (NCI CTCAE) v4.03 ([Appendix 2](#)). A cycle will be considered complete after administration of 1 dose of MEDI-575 for all cycles.

**Table 4.5.4.3-1 MEDI-575 Dose Modification Table**

Hematologic or Nonhematologic Toxicity Attributable to MEDI-575 alone	Dose Modification of MEDI-575
≤ Grade 1	None
Grade 2	
MEDI-575 may be withheld for up to 21 days until resolution to ≤ Grade 1 or baseline and resume at current dose level after discussion with the medical monitor. If subjects experience Grade 2 toxicities that are clinically manageable MEDI-575 may be continued at the current dose and schedule following consultation with the medical monitor. Grade 2 electrolyte abnormalities that can be alleviated through electrolyte replacement do not require dose delay or reduction.
 
Discontinue MEDI-575 if withheld for > 21 days without resolution of toxicity to ≤ Grade 1 or baseline unless clearly attributable to another cause such as disease progression, concomitant therapy or accident.

Grade 3 or 4	
First Occurrence:
 
Withhold MEDI-575 for up to 21 days until resolution to ≤ Grade 1 or baseline. Restart MEDI-575 at 50% of the starting dose.
 
Subjects who experience Grade 3 or Grade 4 laboratory abnormalities or AEs without associated clinical findings that resolve to ≤ Grade 1 or baseline within 21 days will not require dose modification or discontinuation
 
Discontinue MEDI-575 if withheld for > 21 days without resolution of toxicity to ≤ Grade 1 or baseline.
 
Second Occurrence:
 
Discontinue MEDI-575.

#### 4.5.5 Concomitant Medications

Use of concomitant medications, including over-the-counter medications, herbal supplements, and vitamins from the first day of administration of MEDI-575 through 30 days after the last dose is discouraged. However, subjects may receive medications as supportive care or to treat AEs as deemed necessary by the investigator or the subject's physician.

All concomitant medications given to the subject from the time of signing of the informed consent form (ICF) through 30 days after the last dose of MEDI-575 will be recorded in the source document.

#### 4.5.6 Treatment Compliance

Investigational product is administered by study site personnel who will monitor compliance.

## **4.6 Subject Completion**

An individual subject will be considered to have completed the study if followed through the end of the study (defined as 9 months after the last subject has entered the trial or when the sponsor stops the study), regardless of the number of doses of treatment received. Subjects who demonstrate stable disease or better may continue to receive MEDI-575 after study completion following further consultation with the sponsor. Subjects will be considered to not have completed the study if consent was withdrawn or the subject was lost to follow-up (see Section 4.2.3).

## **4.7 End of the Study**

End of the study (“study completion”) is defined as the date of the last protocol-specified visit/assessment (including telephone contact) for the last subject in the study. This date will be 9 months after the last subject is entered into the trial or when the sponsor stops the study. All materials or supplies provided by the sponsor will be returned to the sponsor or designee upon study completion as directed by the site monitor. The investigator will notify the IRB/IEC when the study has been completed.

# **5 Assessment of Efficacy and Clinical Pharmacology**

## **5.1 Efficacy and Clinical Pharmacology Parameters**

The efficacy profile for MEDI-575 will be assessed using PFS-6, time to response (TTR), duration of response (DR), time to progression (TTP), PFS, and OS (see Section 7.3.2).

## **5.2 Schedule of Study Procedures**

All subjects who are assigned an SID number and receive any treatment will be followed according to the protocol regardless of the number of doses received, unless consent is withdrawn. The investigator must notify the sponsor or designee of deviations from protocol visits or evaluations and these evaluations, if applicable, must be rescheduled or performed at the nearest possible time to the original scheduled visit. Protocol deviations will be recorded in the source document with an explanation for the deviation and any study-specific electronic case report forms (eCRFs) or logs designated for capturing protocol deviations, if

applicable for the study. The investigator must comply with the applicable requirements related to reporting of protocol deviations to the IRB/IEC.

Subjects/legal representatives will be instructed to call study personnel to report any abnormalities during the intervals between study visits and to come to the study site if medical evaluation is needed and the urgency of the situation permits. For emergency and other unscheduled visits to a medical facility other than the study site, medical records will be obtained by the investigator and made available to the sponsor or designee during monitoring visits.

Schedules of study procedures for the screening and treatment period as well as the follow-up period are presented in [Table 5.2-1](#) and [Table 5.2-2](#) , respectively, followed by a description of each visit. A description of the study procedures is included in [Section 5.3](#)

**Table 5.2-1 Schedule of Study Procedures: Screening and Treatment Period**

Procedure	Screening	Treatment Period Cycle 1			Cycles $\geq$ 2	Every 2 Cycles, Beginning With Cycle 3	Treatment Discontinuation
	Day -28 to Day -1	Day 1	Day 8	Day 15	Day 1 (+7 days)	Day 1 (-7 days)	
Written informed consent and HIPAA/assignment of SID number	X						
Verify eligibility criteria	X						
Medical history	X						
Physical examination	X	X			X		X
Weight (-1 day allowed)	X	X			X		X
Height	X						
Vital signs	X	X			X		X
Serum chemistry (-1 day allowed)	X	X	X	X	X		X
Hematology (-1 day allowed)	X	X	X	X	X		X
Coagulation parameters (-1 day allowed)	X	X			X		X
Routine urinalysis (-1 day allowed)	X	X	X	X	X		X
Serum pregnancy test	X						
Urine pregnancy test		X			X		
12-lead ECG	X						X
12-lead ECG prior to infusion		X			X		
12-lead ECG post infusion (+ 5 minutes)		X					

**Table 5.2-1 Schedule of Study Procedures: Screening and Treatment Period**

Procedure	Screening	Treatment Period Cycle 1			Cycles $\geq$ 2	Every 2 Cycles, Beginning With Cycle3	Treatment Discontinuation
	Day -28 to Day -1	Day 1	Day 8	Day 15	Day 1 (+7 days)	Day 1 (-7 days)	
ECOG Performance Status	X	X			X		X
PRO: EORTC QLQ-C30 (-3 days allowed)	X	X			X		X
PRO: EORTC QLQ-BN20 (-3 days allowed)	X	X			X		X
Mandatory archived tumor sample	X						
Anti-MEDI-575 antibodies		X			X		X
MEDI-575 serum concentration		X	X	X	X		X
Circulating soluble proteins	X	X	X	X	X		X
Circulating apoptotic markers	X	X		X	X		X
Circulating mRNA/miRNA	X		X				X
DNA analysis (optional)	X						
MRI scan	X					X	X
Assessment of AEs/SAEs	X	X	X	X	X		X
Concomitant medications	X	X	X	X	X		X

**Table 5.2-1 Schedule of Study Procedures: Screening and Treatment Period**

Procedure	Screening	Treatment Period Cycle 1			Cycles $\geq$ 2	Every 2 Cycles, Beginning With Cycle 3	Treatment Discontinuation
	Day -28 to Day -1	Day 1	Day 8	Day 15	Day 1 (+7 days)	Day 1 (-7 days)	
MEDI-575 administration		X			X		
Optional tumor tissue sample							X

AE = adverse event; DNA = deoxyribonucleic acid, ECG = electrocardiogram, ECOG = Eastern Cooperative Oncology Group, EORTC = European Organization of Research and Treatment of Cancer, HIPAA = Health Insurance Portability and Accountability Act, mRNA = messenger ribonucleic acid; miRNA = micro ribonucleic acid; MRI = magnetic resonance imaging, PRO = patient reported outcomes, QLQ = quality of life questionnaire; RNA = ribonucleic acid; SAE = serious adverse event ; SID = subject identification

**Table 5.2-2 Schedule of Study Procedures: Follow-up Period**

Procedure	Follow-up/Post Therapy	
	30-Days After Last Dose (+ 3 days) 60-Days After Last Dose (± 5 days) 90-Days After Last Dose (± 5 days)	Every 3-Months After Last Dose (±2 weeks)
Physical examination	X	X (focused physical exam)
12-lead ECG	X (30-day post visit only)	
Vital signs, including weight	X	
Hematology	X	
Serum chemistry	X	
Routine urinalysis	X	
Urine pregnancy test	X (90-day post visit only)	
AE/SAE assessment	X	
Concomitant medications	X (30-day post visit only)	
MRI scan		X
ECOG Performance Status	X	X
Subsequent anticancer therapy	X	X
Survival status	X	X
MEDI-575 serum concentration	X	
Anti-MEDI-575 antibodies	X	X (first 3-month visit only)
Circulating soluble proteins	X	
Circulating apoptotic markers	X	

AE = adverse event; ECG = electrocardiogram, ECOG = Eastern Cooperative Oncology Group; MRI = magnetic resonance imaging; SAE = serious adverse event

### **5.2.1 Screening (All Subjects)**

All screening procedures must be performed within 28 days prior to the first dose of treatment (Day -28 to Day -1), unless otherwise specified. The screening evaluations may be carried out over more than one visit. Written informed consent and any locally required authorization (eg, HIPAA in the USA, EU Data Privacy Directive authorization in the EU) must be obtained prior to performing any protocol-specified procedures, including screening evaluations. However, if evaluations that have been performed for other purposes prior to informed consent are otherwise suitable for use as screening evaluations, those evaluations need not be repeated if the subject/legal representative consents to allow use. The following evaluations/procedures will be performed during screening:

- 1) Obtain written informed consent and appropriate privacy act document authorization
- 2) Assign an SID number via IWRS
- 3) Verify eligibility criteria
- 4) Obtain medical history
- 5) Perform complete physical examination
- 6) Obtain vital signs, including height and weight (-1 day allowed for weight)
- 7) Obtain 12-lead ECG
- 8) Collect blood samples for:
  - Serum chemistry (-1 day allowed)
  - Hematology (-1 day allowed)
  - Coagulation parameters (-1 day allowed)
  - Serum pregnancy test
  - Circulating soluble proteins
  - Circulating apoptotic markers
  - Circulating messenger ribonucleic acid (mRNA)/microRNA (miRNA)
  - DNA analysis (optional)
- 9) Collect urine for screening sample (-1 day allowed)
- 10) Collect archive tissue for biomarker screening sample
- 11) Measure tumors using MRI
- 12) Assess for AEs and SAEs
- 13) Record concomitant medications

- 14) Assess for ECOG performance status
- 15) Administer Patient Reported Outcome (PRO) questionnaires (-3 days allowed):
  - European Organization of Research and Treatment of Cancer (EORTC) quality of life questionnaire (QLQ)-C30
  - EORTC QLQ-BN20
- 16) Enroll subject if all eligibility criteria are met

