#### **4.2.2 Exclusion Criteria**

Any of the following would exclude the subject from participation in the study:

- 1) Treatment with any investigational agent 30 days prior to study entry
- 2) Concurrent enrollment in another clinical study involving an investigational agent
- 3) Employees of the clinical study site or any other individuals involved with the conduct of the study, or immediate family members of such individuals
- 4) Any chemotherapy, radiotherapy, immunotherapy, biologic, or hormonal therapy for treatment of cancer within 30 days prior to study entry
- 5) Previous mAb treatment specifically directed against PDGF or PDGF receptors
- 6) Previous bevacizumab or other VEGF and anti-angiogenic treatment
- 7) More than 1 recurrence of GBM
- 8) Any surgery (not including minor diagnostic procedures) within 2 weeks prior to baseline disease assessments; or not fully recovered from any side effects of previous procedures
- 9) History of serious allergy or reaction to any component of the MEDI-575 formulation
- 10) New York Heart Association  $\geq$  Grade 2 congestive heart failure within 6 months prior to study entry (see [Appendix 3](#))
- 11) Uncontrolled or significant cardiovascular disease, including:
  - Myocardial infarction and transient ischemic attack or stroke within 6 months prior to enrollment
  - Uncontrolled angina within 6 months

- Diagnosed or suspected congenital long QT syndrome
  - Any history of clinically significant ventricular arrhythmias (such as ventricular tachycardia, ventricular fibrillation, or Torsades de pointes);
  - Clinically significant abnormality on electrocardiogram (ECG)
- 12) History of other invasive malignancy within 5 years prior to study entry except for cervical carcinoma *in situ* (CIS), non-melanomatous carcinoma of the skin or ductal carcinoma *in situ* (DCIS) of the breast that have been surgically cured
  - 13) Any evidence of active infection requiring the use of systemic antimicrobial treatment within 72 hours prior to initial treatment with MEDI-575
  - 14) History of active human immunodeficiency virus or active hepatitis B or C viral infection will be excluded to eliminate the risk of increased AEs due to immune compromise.
  - 15) Systemic immunosuppressive therapy. Subjects taking corticosteroids must be on a stable dose for 7 days prior to initiation of treatment with MEDI-575
  - 16) Presence of extracranial metastatic or leptomeningeal disease
  - 17) Pregnancy or lactation

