## **5.2.2 Treatment Period**

### **5.2.2.1 Cycle 1, Day 1: First Infusion**

The following evaluations will be performed on Day 1 of Cycle 1:

- 1) Perform directed physical examination (if applicable, record new findings as AEs or SAEs)
- 2) Assess for AEs and SAEs since screening visit
- 3) Update concomitant medications
- 4) Obtain vital signs (temperature, blood pressure, pulse, respiratory rate) including weight prior to infusion (-1 day allowed for weight)
- 5) Assess ECOG performance status
- 6) Collect blood for baseline samples prior to infusion:
  - Serum chemistry (-1 day allowed)
  - Hematology (-1 day allowed)
  - Coagulation parameters (-1 day allowed)
  - Anti-MEDI-575 antibodies
  - MEDI-575 serum concentration
  - Circulating soluble proteins
  - Circulating apoptotic markers
- 7) Collect urine for routine urinalysis and urine pregnancy test; ensure result is negative (-1 day allowed)
- 8) Perform 12-lead ECG prior to infusion and post infusion (+ 5 minutes)
- 9) Administer PRO questionnaires (-3 days allowed)
  - EORTC QLQ-C30
  - EORTC QLQ-BN20

- 10) Administer MEDI-575 infusion
- 11) Obtain vital signs at the end of the infusion ( $\pm$  5 minutes) and 30 minutes post-completion of infusion ( $\pm$  5 minutes)
- 12) Obtain blood for PK analysis:
  - MEDI-575 serum concentration: immediately post-completion of infusion ( $\pm$  5 minutes)

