### 5.3.8 Estimate of Volume of Blood to Be Collected

No more than 35 mL of blood will be drawn on a per-day basis across all tests combined on days in which blood is collected. The estimated volume of blood to be collected during the first treatment cycle is 115 mL whereas 30 mL will be collected during every subsequent cycle. The total volume to be collected for all subjects will depend on the number of cycles administered and the length of follow-up.

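### The only pre-dose mRNA/miRNA sample is drawn at screening, so its change to Day 8 can mix recovery from prior therapy with drug effect

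*Protocol*

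**What the plan says.** **Sampling times.** Section 5.2.1 includes "Circulating messenger ribonucleic acid (mRNA)/microRNA (miRNA)" in the screening blood list. The row "Circulating mRNA/miRNA" in Table 5.2-1 is marked at Screening, Cycle 1 Day 8 and Treatment Discontinuation only. The visit lists in Sections 5.2.1 to 5.2.5 agree with the table.

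**Screening window.** Section 5.2.1: "All screening procedures must be performed within 28 days prior to the first dose of treatment (Day -28 to Day -1)."

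**Day 1 baseline for the other markers.** Section 5.2.2.1 instructs sites: "Collect blood for baseline samples prior to infusion." Its list includes soluble proteins and apoptotic markers, both already drawn at screening, but not mRNA/miRNA.

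**Washout.** Section 4.2.2, criterion 4, excludes "Any chemotherapy, radiotherapy, immunotherapy, biologic, or hormonal therapy for treatment of cancer within 30 days prior to study entry." Section 4.3 defines entry as the IWRS assignment once eligibility is confirmed, and adds: "MEDI-575 must be administered within 48 hours after treatment assignment." Criterion 15 requires a stable corticosteroid dose for the 7 days before treatment starts.

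**Use of the samples.** Sections 5.3.5 and 7.3.3.2 say that whole-blood mRNA profiling may be done, to relate inhibition of PDGF-related genes to clinical activity and other circulating factors. Section 5.3.5 also allows miRNA profiles before and after dosing. These analyses are exploratory and descriptive.

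**The concern.** A change from baseline isolates a drug effect only if little else changes between the two samples. Here the baseline may be four weeks old at first dose, and its age varies between subjects. Every subject has had radiotherapy and temozolomide (Section 4.2.1, criterion 4), and the washout protects the dosing date rather than the sampling date. A whole-blood expression profile taken soon after such treatment may differ from one taken a month later for reasons unrelated to MEDI-575.

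Steroids raise the same problem. The 7-day stability rule covers a Day 1 sample but not a screening sample drawn before those 7 days, so a dose change after the draw is permitted.

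The study has a single arm, so no comparison group can separate these influences from the drug. Nor can the analysis recover a clean baseline later, because no Day 1 RNA sample will exist. What is at stake is the interpretability of one exploratory biomarker.

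**Working it through.** The plan gives no figure of its own for this interval, so the check is timing arithmetic from its rules.

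**Inputs**
- Washout before entry: 30 days (Section 4.2.2, criterion 4).
- Entry to first dose: 0 to 2 days (Section 4.3).
- Screening sample: *s* days before first dose, *s* = 1 to 28 (Section 5.2.1).
- Day 8: 7 days after first dose, since first dose is Day 1 (Section 4.5.4).

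**Formulas**
- Shortest time from prior therapy to sample = 30 + (0 to 2) − *s*.
- Sample to Day 8 = *s* + 7.
- Share of that interval before any MEDI-575 = *s* / (*s* + 7).

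| Sample taken | Shortest time since therapy (days) | Sample to Day 8 (days) | Share before any drug |
|---|---|---|---|
| Day -28 | 2 to 4 | 35 | 28/35 = 80% |
| Day -21 | 9 to 11 | 28 | 21/28 = 75% |
| Day -14 | 16 to 18 | 21 | 14/21 = 67% |
| Day -7 | 23 to 25 | 14 | 7/14 = 50% |
| Day -1 | 29 to 31 | 8 | 1/8 = 12.5% |
| Cycle 1 Day 1, pre-infusion (*s* = 0) | 30 to 32 | 7 | 0% |

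**Does the washout really overlap screening?** Section 4.3 gives the only explicit definition of entry, and Section 5.2.1 puts enrollment last in the screening list. Section 4.2 requires consent before screening evaluations or medication washouts, which fits a washout running during screening. If entry meant consent instead, a sample drawn after consent would be at least 30 days after therapy. The interval to Day 8 of up to 35 days would stand either way.

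**Room for the sample on Day 1.** Section 5.3.8 caps each day at 35 mL and estimates that "30 mL will be collected during every subsequent cycle." Scheduled blood in those cycles is drawn on Day 1 only, from the same panel as Cycle 1 Day 1, so the suggested room is 35 − 30 = 5 mL. This is rough. The section's first-cycle estimate of 115 mL exceeds three Cycle 1 draw days at the cap (3 × 35 = 105 mL), so it can only hold if screening blood is counted too.

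**The case against.** The strongest reply is that nothing here is an error. The table and visit lists agree, and the choice affects no endpoint, dose decision or success criterion. The profiling is optional, and the protocol never commits to a screening-to-Day-8 change for blood mRNA. The named pharmacodynamic marker is PDGF-AA, and circulating soluble proteins already have a Day 1 pre-infusion sample. All of this stands, and it limits the weight of the point.

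A reader might infer that the Day 8 change will be confounded in general, or that a recovery effect would be reported as a drug effect. The documents do not support that. The worst case needs both therapy at the minimum washout and a draw on Day -28. A sample drawn near Day -1, or long after prior therapy, is little affected. Screening may span several visits, and nothing says how many subjects would be near the extreme.

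The steroid concern is also limited. Criterion 15 fixes the dose for the last 7 days, and Section 4.5.5 has concomitant medications recorded from consent, so later changes can be identified. Changes before that week remain possible.

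Finally, a Day 1 baseline is no complete cure: a 7-day uncontrolled change can still include some recovery or disease progression.

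**Conclusion.** The point holds as a minor, inexpensive improvement in sampling design. Circulating mRNA/miRNA is the only repeatedly sampled circulating biomarker without a pre-infusion Day 1 draw, and the protocol gives no reason. In the permitted worst case its baseline is 2 to 4 days after prior therapy and 35 days before Day 8, with 80% of that interval before any drug. The Day 8 change *can* mix recovery or steroid changes with drug effect, and a single-arm study has no comparison group to separate them.

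The figure of 2 to 4 days rests on the Section 4.3 definition of entry and on therapy at the minimum washout. The variable baseline age, and an interval of 8 to 35 days instead of 7, depend on neither. PFS-6 and the other clinical endpoints are untouched.

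**What to change.** In Table 5.2-1 and Sections 5.2.1 and 5.2.2.1, move the mRNA/miRNA sample from screening to Cycle 1 Day 1 before the infusion, alongside the soluble-protein and apoptotic-marker samples, and name it as the baseline. Every treated subject sampled on schedule would then have a baseline at least 30 to 32 days after anticancer therapy, inside the steroid-stable period, and 7 days before the Day 8 sample.

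The move adds no visit and no extra sample, and screening failures no longer give this blood. It does make the Day 1 draw larger. A reader might call the change free, but the protocol states neither the volume nor the number of tubes. The sponsor should first confirm against the laboratory manual that the sample fits the 35 mL daily limit; the estimated panel suggests about 5 mL of room.
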